6.4 Prohibited medications

Any concurrent use of immunosuppressive therapies including but not limited to the following:

- Anti-IL-6, anti-IL-6R antagonists or Janus kinase inhibitors (JAKi);
- Anakinra; canakinumab; abatacept; tumor necrosis factor (TNF) inhibitors
- Cell-depleting agents (e.g., anti CD20)
- Alkylating agents including cyclophosphamide (CYC);
- Cyclosporine (CsA), azathioprine (AZA) or mycophenolate mofetil (MMF) or leflunomide or methotrexate

6.5 Participant numbering

Each participant is identified in the study by a Participant Number (Participant No.), that is assigned when the participant is enrolled for screening and is retained for the participant throughout his/her participation in the trial. The Participant No. consists of the Center Number (Center No.) (as assigned by the Promoter to each of the investigative sites) with a sequential participant number suffixed to it, so that each participant's participation is numbered uniquely across the entire database. Upon signing the informed consent (ICF) form, the participant is assigned to the next sequential Participant No. available.

6.6 Treatment assignment, randomization

At Randomization visit, all eligible subjects will be randomized via Interactive Response Technology (IRT) to one of the treatment arms. A designated site staff member other than the investigator or study staff involved in safety and efficacy assessments or eCRF completion will contact the IRT after confirming that the subject fulfills all the inclusion/exclusion criteria. The IRT will assign a randomization number to the participant, which will be used to link the participant to a treatment arm.

6.7 Treatment blinding

This is a randomized double-blind placebo-controlled treatment trial. Participants, all site staff (including study investigator and study nurses) and persons performing the assessments will remain blind to the identity of the treatment from the time of randomization until database lock. Unblinding a single participant at site for safety reasons (necessary for participant management) will occur after discussion with the Promoter.

Drug product will be supplied in bulk, so an unblinded pharmacist/nurse who is independent of the study team will be required in order to maintain the blind. This unblinded pharmacist/nurse will receive the treatment arm assigned by the IRT system during the randomization transaction. Appropriate measures will be taken by the unblinded pharmacist/nurse to ensure that the treatment assignments are concealed from the rest of the site staff.

The independent DSMB will be allowed to access treatment information via a request to the randomization office for the purpose of creating, reviewing and assessing blinded interim results.

All unblinded personnel will otherwise keep randomization lists and data or information that could unblind other study team members confidential and secure until clinical database lock. Following final database lock all roles may be considered unblinded.

6.8 Additional treatment guidance

Recommended treatment of adverse events

At present there is insufficient information to provide specific recommendations regarding treatment of adverse events (AEs) in this patient population. Medication used to treat adverse events (AEs) must be recorded on the appropriate CRF.

Emergency breaking of assigned treatment code

Emergency code breaks must be undertaken only when it is required to in order to treat the participant safely. Blinding codes may also be broken after a participant discontinues treatment due to disease progression if deemed essential to allow the investigator to select the participant's next treatment regimen, and after discussion and agreement with the promoter. Most often, study treatment discontinuation and knowledge of the possible treatment assignments are sufficient to treat a study participant who presents with an emergency condition. Emergency treatment code breaks are performed using the IRT after discussing it with the Promoter. When the investigator contacts the system to break a treatment code for a participant, he/she must provide the requested participant identifying information and confirm the necessity to break the treatment code for the participant. The investigator will then receive details of the investigational drug treatment for the specified participant.

In addition, oral and written information to the participant must be provided on how to contact his/her backup in cases of emergency, or when he/she is unavailable, to ensure that un-blinding can be performed at any time.

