10.1 Definition of adverse events and reporting requirements

According to Regulation (EU) No 536/2014 of the European Parliament and of the council of 16 April 2014 for definition of adverse events, adverse reactions and reporting including causality. For the purpose of this protocol adverse events are classified into the following categories:

Adverse events

An adverse event (AE) is any untoward medical occurrence (e.g. any unfavorable and unintended sign [including abnormal laboratory findings], symptom or disease) in a clinical investigation participant after providing written informed consent for participation in the study. Therefore, an AE may or may not be temporally or causally associated with the use of a medicinal (investigational) product.

The investigator has the responsibility for managing the safety of individual participant and identifying adverse events. The Promoter will be readily available to advise on trial related medical questions or problems.

The occurrence of adverse events must be sought by non-directive questioning of the participant at each visit during the study. Adverse events also may be detected when they are volunteered by the participant during or between visits or through physical examination findings, laboratory test findings, or other assessments.

Adverse events must be recorded under the signs, symptoms, or diagnosis associated with them, accompanied by the following information (as far as possible):

- 1. Severity grade:
 - mild: usually transient in nature and generally not interfering with normal activities
 - moderate: sufficiently discomforting to interfere with normal activities
 - severe: prevents normal activities
- 2. Its relationship to the study treatment. If the event is due to lack of efficacy or progression of underlying illness (i.e. progression of the study indication) the assessment of causality will usually be 'Not suspected.' The rationale for this guidance is that the symptoms

of a lack of efficacy or progression of underlying illness are not caused by the trial drug, they happen in spite of its administration and/or both lack of efficacy and progression of underlying disease can only be evaluated meaningfully by an analysis of cohorts, not on a single participant

- 3. Its duration (start and end dates) or if the event is ongoing, an outcome of not recovered/not resolved must be reported
- 4. Whether it constitutes a serious adverse event (SAE) and which seriousness criteria have been met

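### Emergency unblinding must follow a discussion with the Promoter, with no exception for urgency, which sits badly with the protocol's aim that the code can be broken at any hour

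*Protocol*

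**What the plan says.** Protocol section 6.7 (Treatment blinding) keeps participants, site staff and assessors blind until the database is locked, then provides for an exception: "Unblinding a single participant at site for safety reasons (necessary for participant management) will occur after discussion with the Promoter".

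Section 6.8 (Emergency breaking of assigned treatment code) makes four statements that bear on the same step:

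- On when a break is justified: "Emergency code breaks must be undertaken only when it is required to in order to treat the participant safely".
- On how it is done: "Emergency treatment code breaks are performed using the IRT after discussing it with the Promoter". The investigator then identifies the participant to the system, confirms that the break is necessary, and receives the allocation.
- On access: participants must be told how to reach the investigator's backup, "to ensure that un-blinding can be performed at any time".
- On a second, non-emergency route: "Blinding codes may also be broken after a participant discontinues treatment due to disease progression if deemed essential". This is to help choose the participant's next regimen, "and after discussion and agreement with the promoter".

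Section 10.1 adds a general statement on the Promoter: "The Promoter will be readily available to advise on trial related medical questions or problems".

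**The concern.** An emergency code break exists for the case in which the treating physician needs the allocation quickly. Here the written sequence puts a conversation with a third party first, in a multicenter trial where the treating physician may not be at the Promoter's institution. A site that follows the text literally and cannot reach the Promoter has no sanctioned way forward. It must either wait or deviate from the protocol.

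The allocation can matter to the treating team. Section 6.3 warns of severe immune-suppression if certain rescue agents are given together with the investigational drug, and that risk depends on the arm. Section 4.2 expects inhibition of the receptor pathway for at least three weeks at doses of 3 mg/kg or more, so the question remains open well after the infusion ends.

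What is at stake is timely access to the allocation for an individual patient. The validity of the trial's result is not in question.

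**Working it through.** No arithmetic applies. The rule depends on no error rate, effect size, event count or sample size, so the check is a comparison of the texts.

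1. **Is the condition really prior, and is it general?** Yes. Sections 6.7 and 6.8 both place the unblinding after the discussion. Section 6.7 applies this to safety unblinding needed to manage a participant, and section 6.8 to emergency breaks. Neither contains an exception for urgency or for failed contact.

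2. **Does another section relax it?** No. Section 9.1 deals with what follows emergency unblinding (discontinuation of study treatment, registration in the IRT) and does not touch the order of steps. Section 10.1 describes the Promoter's general availability for medical questions. It is not linked to code breaks and does not say what to do if contact fails.

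3. **Does the system need the discussion?** Not on the text. As described in section 6.8, the IRT step requires participant identification and confirmation of necessity, after which the allocation is released. The possible delay therefore comes from the wording of the procedure.

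4. **Can the condition and the stated aim both be met?** If the Promoter is reachable, yes: the discussion happens and the code is broken. If the Promoter is not reachable, no: the condition in 6.7 and 6.8 cannot be satisfied, so the aim of access at any hour fails. The inconsistency is confined to that second case, which is the case an emergency procedure has to cover.

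5. **How strong is the condition?** The two routes in section 6.8 are worded differently. The progression route needs discussion and agreement; the emergency route needs discussion only. The difference implies that in an emergency the Promoter is consulted and does not decide.

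6. **Does the progression route fit the design?** Poorly. Section 6 provides for one dose, and section 6.1 for an infusion of about one hour. Once it is complete, no treatment remains to be discontinued, so the trigger has no clear meaning for a patient who worsens on a later day.

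**The case against.** The strongest defence has four parts.

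- **No veto.** A reader might infer that the Promoter can block an emergency break. The text does not support that: agreement is required only for the progression route. This stands, and it limits the point to sequence and delay.

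- **Different subject.** The words about access at any time belong to a sentence on telling participants how to reach the investigator's backup. They are not a second rule on the same step. This also stands. The conflict is between a stated purpose and a procedure that can defeat it, which is weaker than two directly opposed rules but still needs reconciling.

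- **Promoter availability.** Section 10.1 describes a readily reachable Promoter. A reader might go further and say the plan lacks a round-the-clock contact. That cannot be held against it, because contact pages were removed from the text under review. Availability makes the failure less likely; it does not supply the missing exception.

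- **Allocation seldom needed.** Section 6.8 says that stopping treatment and knowing the possible assignments will usually suffice. Section 9.1 requires the infusion to be interrupted for severe hypersensitivity whatever the arm, and section 6.3 already makes investigational COVID-19 treatments in worsening patients subject to Promoter approval. These reduce how often the rule would bite. The first is of limited help after the infusion, since the option of stopping treatment has then gone.

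**Conclusion.** The point holds in a limited form. Sections 6.7 and 6.8 fix a sequence for emergency unblinding that has no exception and cannot be squared with the stated aim when the Promoter is unreachable. It applies in principle to every one of the approximately 50 patients. Delay to urgent care is an inference from the prescribed order, not something the documents report, and they offer no basis for putting a frequency on it. Sample size and analysis are unaffected. This is an inexpensive correction to the wording that should be made for participant safety; it is not a flaw that undermines the trial.

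Two stronger readings are not supported.

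- **Size of the progression route.** A reader might take the assumptions in section 11.1 (83% and 40% off oxygen by day 14) and compute 25 × 0.17 + 25 × 0.60 = 4.25 + 15, or about 19 patients exposed to unblinding and so to bias in the primary endpoint. That figure counts patients assumed not to be off oxygen by day 14. Such a patient may be stable or improving and need not have progressed. The route also requires that the break be judged essential and that the Promoter agree. No number of such code breaks, and no size of bias, follows from the documents.

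- **Conflict with the general blinding rule.** Section 6.7 says that site staff "will remain blind to the identity of the treatment from the time of randomization until database lock", and a reader might see any later code break as contradicting this. The next sentence of 6.7 already provides for single-participant unblinding, and a general rule with stated exceptions is ordinary drafting.

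What remains of the progression route is a secondary drafting fault: a trigger that does not suit a single infusion.

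**What to change.** Reconcile sections 6.7 and 6.8 with one rule: in an emergency the investigator or the backup may break the code directly in the IRT at any time, the Promoter is informed promptly afterwards, and the reason, date and time are recorded. Prior discussion can remain as an encouragement where time allows, but should not be a condition.

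Separately, delete the progression route in section 6.8, or redefine its trigger so that it has a clear meaning after a completed single infusion.

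The cost is a wording amendment and, if the system currently enforces the prior contact, a change to an IRT permission. The small downside is that the Promoter learns of an emergency break after it has happened.

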6.9 Preparation and dispensation

Each study site will be supplied with study drug. Clinical lots of KPL-301 drug product and corresponding diluent/placebo are manufactured in accessorized pre- filled syringes (APFS). The drug product presentation has a matching placebo. The deliverable or extractable volume for APFS is 1.0 mL. The Pharmacy Manual contains all the information about drug preparation. APFS are to be stored by the GMP pharmacy facility and investigator at 2-8 degrees Celsius at which temperature the product is viable until its listed expiry date.

Individual patient infusions are to be prepared at the investigational site under the authority of the investigator and in accordance with local regulations. Preparation of the investigational drug must be done in a separate space/room where study personnel have no access during time of preparation.

The investigational product is to be diluted using the acetate buffer which will be provided. Doses are to be prepared for administration via a syringe driver depending upon the final diluted volume to be administered. Individual dilutions for administration to patients are to be prepared on the day of administration and administered within 4 hours.

Study treatment must be received by a designated person at the study site, handled and stored safely and properly and kept in a secured location to which only the designated site personnel have access. Upon receipt, all study treatment will be stored according to the instructions specified in the [IB].

Clinical supplies are to be dispensed only in accordance with the protocol. Study treatment will be prepared by an independent pharmacist or qualified site personnel in order to ensure treatment blinding as described above. At the conclusion of the study, and as appropriate during the course of the study, the investigator will return or destroy all unused study treatment, packaging, drug labels. The investigator will retain a copy of the completed drug accountability log.

7. Informed consent procedures

Eligible participants may only be included in the study after providing Institutional Review Board (IRB)/ Independent Ethics Committee (IEC)-approved informed consent.

If applicable, in cases where the participant's representative(s) gives consent (if allowed according to local requirements), the participant must be informed about the study to the extent possible given his/her understanding. If the participant is capable of doing so, he/she must indicate agreement by personally signing and dating the written informed consent document.

Informed consent must be obtained before conducting any study-specific procedures (e.g. all of the procedures described in the protocol). The acquisition of informed consents and information forms should be documented in the patient's medical records, as required by ICH GCP, and the information and informed consent forms should be signed and personally dated by the patient, or a legally acceptable representative, and by the physician who conducted the information and informed consent discussion. The original signed information and informed consent forms should be retained in accordance with institutional policy, and a copy of the signed forms should be provided to the patient or legally acceptable representative.

All patients will be informed of the aims of the study, the potential benefit, the possible adverse events, the procedures and possible hazards to which he/she will be exposed, and the mechanism of treatment. It will be emphasized that the participation is voluntary and that the patient is allowed to refuse further participation in the protocol, whenever he/she wants. This will not prejudice the patient's subsequent care. They will be informed as to the strict confidentiality of their data, but that their medical records may be reviewed for trial purposes by authorized individuals other than their treating physician. This must be done in accordance with the local regulatory requirement

Regulatory authorities and/or IEC/IRB may request access to all source documents, data capture records, and other study documentation for one-site audit or inspection. Direct access to these documents must be guaranteed by the investigator, who must provide support at all times for these activities.

The patient's confidentiality will be maintained and will not be made publicly available to the extent permitted by the applicable laws and regulations (Low n. 675/1996 and amendments)

and Regulation (EU) 2016/679 of the European Parliament and of the Council of 27 April 2016 on the protection of natural persons with regard to the processing of personal data and on the free movement of such data, and repealing Directive 95/46/EC (General Data Protection Regulation).

The name of the patient will not be asked by the promoter. A identification number will be automatically attributed to each patient enrolled in the trial. This number will identify the patient and must be included on all case report forms. In order to avoid identification errors, date of birth will also be reported on forms.

Information about common side effects already known about the investigational drug can be found in the Investigator's Brochure (IB). This information is included in the participant informed consent and should be discussed with the participant during the study as needed. Any new information regarding the safety profile of the investigational drug that is identified between IB updates will be communicated. New information might require an update to the informed consent and then must be discussed with the participant.

Women of childbearing potential must be informed that taking the study treatment may involve unknown risks to the fetus if pregnancy were to occur during the study and agree that in order to participate in the study they must adhere to the contraception requirements.

8. Visit schedule and assessments

The Assessment & Procedures Schedule (Table 1) lists all of the assessments when they are performed. All data obtained from these assessments must be supported in the participant's source documentation.

Participants should be seen or phoned for all visits/assessments as outlined in the assessment schedule (Table 1) or as close to the designated day/time as possible. Missed or rescheduled visits should not lead to automatic discontinuation. At the day of discharge from the hospital, all assessments in Table 1 should be conducted. In addition, contact information for the patient and/or legal representatives should be obtained for the follow-up visits.

Screening assessments are to be taken as indicated in Table 1 prior to dosing and are considered baseline measurements. Patients who meet the inclusion/exclusion criteria may be dosed immediately after obtaining the baseline measurements.

8.1 Schedule of Assessment and Procedures (table 1)

	(0-24 hrs prior to dose)	(investigational drug dosing)	п	hospitalization until day 28 or discharge (whicever is earlier)	7*	14*	28 (or at discharge)*	*34 -/+	(+- 7 days) End of study*
		S	T U D	YPEF	R I O	D		FOLLOW	U P
informed consent	×								
Inclusion/exclusion criteria	×	x(2)							
Demographics / medical history /relevant comorbidities	×								
SarsCoV-2	x(1)	REC	CORD ALL SA	RECORD ALL SARS-COV-2 DETERMINATIONS AS OBTAINED	S AS OBTAIN	ED	×	x (if available)	x (if available)
Vital signs (HR, RR, SpO2 and/or PaO2, BP, body temp)	×	x(2)	×	×	×	х	×		
Oxygen delivery (flow + FiO2)	×	x(2)	×	×	×	×	×	×	×
NIV use (hours/day)	×	x(2)	×	×	×	×	×		
Height, weight	×								
Physical		5(2)	S						
Clinical status with the 7-point ordinal scale		x(2)	×	×	×	×	×	×	×
Vital status (and if applicable, cause of death)			×	×	×	×	×	×	×
Blood cultures (Aer/Anaer)		x(3)							
Hematology (Hb, MCV, WBC, Plt, absolute count of N,L,M,E,B)	×		×	x every other day until discharge	×	×	×	x (if available)	x (if available)
Clinical chemistry (AST, ALT, ALP,									
LDH, creatine kinase, troponin,	>		>	x every other day until	,	>	,	v (if everience)	(aldelieve fi) v
chicoco total protoin CBD forritin	<		<	discharge	<	<	<	v (II available)	A (II available)
glucose, total protein, chr., refritiil, D-dimer; IL-6 [if available])									
Pregnancy test (if applicable)	S								
CT scan / chest X-ray	x(1)		RECORD ALL	RECORD ALL PULMONARY IMAGING AS OBTAINED	OBTAINED		x (if available)		
Electrocardiogram	S(1)								
Adverse events	×	x(2)	×	×	×	×	×	×	×
Prior / concomitant medications	×	x(2)	×	×	×	X	×	×	×
Randomization		x(2)							
Study drug administration		x(2)							
In-hospital outcomes:									
Days on non-invasive ventilation		x(2)	×	 	 	 	×		
Days on mechanical ventilation		x(2)	 	 		 	×		
Days in hospital		x(2)	×	×		×	×		
Days in ICU		x(2)	×	×		×	×		
Days with use of supplemental O2		x(2)	×	×		×	×		
Days on ECMO		x(2)	×	×		×	×		
Blood collection for experimental		x(2)		x (day 5)	x (if	x (if	x (if possible)	x (if possible)	x (if possible)

x to be recorded into the eCRF

for biomarkers will not be conducted (but collected if performed for other indications). If the patient remains hospitalized, however, all assessments noted in the table should be conducted on the visit day noted. * If patient is discharged prior to Day 28, then all assessments listed for Day 28 should be conducted on the day of discharge. Visits at Days 14, 28, 56, 84 should be conducted via phone for patients who were discharged prior to the visit. These phone visits should only collect Clinical status evaluation with 7-point

⁽¹⁾ Results confirming positive SARS-CoV-2 virus by PCR or by other approved diagnostic methodology available within one week;

chest x-ray or CT scan within 4 days prior to randomization may be used for eligibility; ECG in the previous 2 weeks

(2) All assessment at day 0 must be conducted prior to mavrilimumab dosing

(3) Blood cultures are acceptable if taken in the 24 hrs before randomization. At day 0 must be they must be taken prior to mavrilimumab dosing

